9.5 Treatment Overdose

Study treatment overdose is any accidental or intentional use of treatment in an amount higher than the dose indicated by the protocol for that subject. Study treatment compliance should be reviewed to detect potential instances of overdose (intentional or accidental).

Any treatment overdose during the study should be noted on the study medication eCRF.

An overdose is not an AE per se, however all AEs associated with an overdose should both be entered on the Adverse Event eCRF and reported using the procedures detailed in Section 10.3, even if the events do not meet seriousness criteria. If the AE associated with an overdose does not meet seriousness criteria, it must still be reported using the Endo Serious Adverse Event (SAE)/Reportable Event Form and in an expedited manner, but should be noted as nonserious on the form and the Adverse Event eCRF.

9.6 Pharmacokinetics

Not applicable.

9.7 Pharmacodynamics

Not applicable.

9.8 Genetics

Not applicable.

9.9 Biomarkers

9.9.1 Immunogenicity Assessments

Not applicable.

9.10 Medical Resource Utilization and Health Economics

Not applicable.

10. STATISTICAL CONSIDERATIONS AND METHODS

10.1 Sample Size Determination

The proposed sample size is 5 subjects.

10.2 Populations for Analysis

For the purposes of analysis, the following populations are defined:

- The Safety Population will include all subjects who receive at least 1 injection of study treatment. All safety evaluations will be based on the Safety Population.
- The Evaluable Population will include all subjects who receive at least 1 injection of study treatment and have at least 1 I-GAIS evaluation. All efficacy evaluations will be based on the Evaluable Population.

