3. OBJECTIVES AND ENDPOINTS

Objectives	Endpoints
Primary	
	better) score on the Investigator Global Aesthetic Improvement Scale. (I-GAIS) for buttock and thigh
Secondary	
To evaluate effectiveness of CCH-aaes in individuals when concomitantly treating the buttock and the thigh in one treatment session	The proportion of subjects with improved (+1 or better) score on I-GAIS for either buttock or either thigh on Days 22, 43, and 90.
To assess subject satisfaction with CCH treatment of buttock or thigh cellulite in adult females.	Mean change from baseline in Body-Q Appraisal of Cellulite ^d to Day 90.
To generate calculations to determine a matrix of buttock and thigh injections possible from a single 1.84 mg vial	Dilution matrix used in clinical settings.

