8. DISCONTINUATION FROM STUDY TREATMENT AND SUBJECT DISCONTINUATION/WITHDRAWAL

8.1 Discontinuation of Study Treatment

Subjects who discontinue from study treatment or withdraw from the study for any reason after the Day 1 dosing will be encouraged to complete the remaining study visits and evaluations and provide any additional follow-up information as required by the study, unless the subject specifically indicates that they will not participate in any further evaluations. The date of, and reason for, study treatment discontinuation will be recorded.

Permanent study treatment discontinuation is required for the following:

• The subject becomes pregnant during the active treatment phase of the study (Day 1 through Day 43).

Subjects who discontinue from study treatment at any time after the first dose of study drug will not be replaced.

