10.3.1 Efficacy Analysis

The primary efficacy endpoint of the proportion of subjects with improved (+1 or better) score on I-GAIS for either buttock or either thigh at Day 90 will be summarized by cohort using appropriate summary statistics and its 95% confidence interval will be provided.

All secondary and exploratory efficacy endpoints will be summarized using appropriate descriptive statistics by time point and cohort.

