10.4 Interim Analysis

Because of the lower responder rate for thigh (60%) and an anticipated high drop-out rate (10%), an interim data analysis will be done when approximately the first 40 Cohort 1 (thigh) subjects complete their Day 90 assessments. The interim analysis will include the primary endpoint (the proportion of subjects with improved [+1 or better] score on I-GAIS for either thigh at Day 90) and mean change from baseline in Body-Q Appraisal of Cellulite at Day 90 for thigh treated subjects.

Depending on the outcome of the interim analysis for the primary endpoint, the study sample size may be revisited.

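### The efficacy set leaves out treated subjects who are never rated on I-GAIS, so an early loss raises the Day 90 response rate above its all-treated value in a 5-subject trial

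*Protocol*

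**What the plan says.** Protocol Section 10.2 defines two sets. For safety: "The Safety Population will include all subjects who receive at least 1 injection of study treatment". For efficacy: "The Evaluable Population will include all subjects who receive at least 1 injection of study treatment and have at least 1 I-GAIS evaluation". It then fixes the scope of the second set: "All efficacy evaluations will be based on the Evaluable Population". No other efficacy set is defined.

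Section 9.2.7 describes I-GAIS as a comparison of later images with the Day 1 pretreatment image, so there is no baseline rating. Section 3 places the rating at three visits in a secondary endpoint: "score on I-GAIS for either buttock or either thigh on Days 22, 43, and 90". The primary endpoint uses the Day 90 rating. Section 10.3.1 says that the primary proportion "will be summarized by cohort using appropriate summary statistics and its 95% confidence interval will be provided". It plans no hypothesis test.

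On losses, Section 8.1 says: "Subjects who discontinue from study treatment at any time after the first dose of study drug will not be replaced". Sections 8.2 and 8.3 say the same for withdrawal and loss to follow-up. Section 8.1 also encourages subjects who stop to complete the remaining visits, and Section 8.2 asks for Early Termination procedures when a subject leaves.

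Section 10.1 gives the size without a derivation: "The proposed sample size is 5 subjects".

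**The concern.** Membership of the efficacy set depends on something that happens after treatment, namely getting at least one rating. A subject injected on Day 1 who leaves before being rated counts for safety but not for efficacy. Section 10.3 leaves detail to a later statistical analysis plan, but this rule is already fixed in the protocol, and a plan that follows the protocol would carry it forward.

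The rule matters if leaving early is related to how the subject fared. Section 2.3 lists injection-site bruising, swelling and pain as common, and Section 8.2 allows withdrawal for safety reasons, so a link is plausible. The trial is single-arm and open-label, so no control group would offset a favourable selection. The Day 90 proportion and its interval are the whole primary efficacy result, and each of the 5 subjects carries 1/5 = 20 percentage points of it.

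**Working it through.** The protocol gives no basis for the 5 subjects, so there is no figure of its own to reproduce. The check compares two denominators for the same number of responders.

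**Inputs.** N = 5 treated (Section 10.1). Evaluable set = treated and rated at least once (Section 10.2). No replacement (Sections 8.1 to 8.3). Drop-out 10% (Section 10.4, illustration only). Drop-out of 5% and 20% are assumed to show a range.

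**Step 1: effect of an unrated loss.** With x responders and k subjects never rated, the rule reports x/(5 − k). The all-treated rate, counting unrated subjects as not improved, is x/5. The exact (Clopper-Pearson) 95% limits for x out of n are the 0.025 quantile of Beta(x, n − x + 1) and the 0.975 quantile of Beta(x + 1, n − x).

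| Unrated losses | Responders | Evaluable set | All treated | Difference |
|---|---|---|---|---|
| 1 | 1 | 1/4 = 25% | 1/5 = 20% | 5 points |
| 1 | 2 | 2/4 = 50% | 2/5 = 40% | 10 points |
| 1 | 3 | 3/4 = 75% (19.4% to 99.4%) | 3/5 = 60% (14.7% to 94.7%) | 15 points |
| 1 | 4 | 4/4 = 100% (39.8% to 100%) | 4/5 = 80% (28.4% to 99.5%) | 20 points |
| 2 | 3 | 3/3 = 100% (29.2% to 100%) | 3/5 = 60% (14.7% to 94.7%) | 40 points |

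With no responders, both rates are 0%.

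**Step 2: direction.** The differences above are relative to counting the lost subject as not improved. Suppose instead that, in the row with one loss and 3 responders, the lost subject would have responded. The rate with complete data is then (3 + 1)/5 = 80%. The rule's 75% is 5 points too low and the all-treated 60% is 20 points too low. The rule biases upward only if losses fall mainly on subjects who would not have improved.

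**Step 3: chance of a loss.** The chance that at least 1 of 5 is lost is 1 − (1 − d)^5.
- d = 10%: 1 − 0.9^5 = 41%.
- d = 5% (assumed): 23%.
- d = 20% (assumed): 67%.

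These count loss at any time up to Day 90, whereas the rule removes only subjects with no rating at all. If the 10% is assumed to arise at a constant rate over 90 days, the chance of at least one loss before the Day 22 visit, which falls 21 to 28 days after Day 1, is:
- 21 days: 1 − 0.9^(5 × 21/90) = 12%.
- 28 days: 1 − 0.9^(5 × 28/90) = 15%.

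**Step 4: a subject rated only at Day 22.** This subject belongs to the Evaluable Population. If 3 of the other 4 respond at Day 90, the result depends on how the missing Day 90 rating is scored:
- not improved: 3/5 = 60%;
- observed cases only: 3/4 = 75%;
- early response carried forward: 4/5 = 80%.

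The population definition does not choose among these.

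**The case against.** Three stronger readings are tempting, and the documents support none of them.

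- A reader might infer that admitting subjects on a Day 22 rating alone also inflates the Day 90 rate. It does not by itself, because such a subject stays in the denominator (Step 4). The effect depends on the scoring of a missing Day 90 rating, which a protocol may leave to the statistical analysis plan. That the protocol gives no such rule is not a finding.
- A reader might take 41% as the chance that the rule distorts the result. It is an upper bound, since it counts loss at any time. The 10% behind it comes from Section 10.4, which describes an interim analysis after about 40 Cohort 1 subjects and does not fit a 5-subject trial.
- A reader might infer that upward bias is established. Section 4.2 describes most adverse events in earlier studies as mild to moderate and transient, and nothing in the protocol links leaving to outcome.

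The protocol also contains mitigation. Continued visits are encouraged, and Early Termination procedures are required when a subject leaves. The I-GAIS row is not visible in the available text of the Schedule of Activities, so it cannot be settled whether an early leaver would be rated. A subject rated at early termination would be evaluable.

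Finally, the study is exploratory with no success threshold, and the intervals for 3/4 and 3/5 each span about 80 points and largely overlap. All of this stands and lowers the weight of the point. What remains is that a treated subject who is never rated leaves the primary denominator by a rule already fixed in the protocol.

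**Conclusion.** The point holds as a minor improvement. Section 10.2 removes treated but never rated subjects from the primary Day 90 proportion. Relative to counting them as not improved, one such loss raises the reported rate by 5 to 20 points for 1 to 4 responders; the case with 3 responders gives 75% instead of 60%. Calling this upward bias rests on two assumptions: that the subject is not rated at early termination, and that leaving is related to poor tolerability or poor outcome. How often it would happen is not known from the documents. What changes is the reported point estimate and its interval.

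**What to change.** In Section 10.2, base the primary Day 90 I-GAIS proportion on all treated subjects, using the existing Safety Population definition. State that a subject without a Day 90 I-GAIS counts as not improved; the all-treated denominator needs such a scoring rule to be usable. Keep the Evaluable Population result as supportive, so that a reader can see both rates.

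This is a short text change and needs no new subjects, visits or data. The cost is a rate that may be less favourable, by at most 20 points with one unrated loss, and that is conservative if the lost subject would have responded. If no one is lost, both analyses give the same result.

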10.3 Statistical Hypotheses and Analyses

This section provides a general summary of the statistical methods to be used in analyzing study data. A more detailed statistical analysis plan will be developed and finalized prior to the interim analysis.

10.3.1 Efficacy Analysis

The primary efficacy endpoint of the proportion of subjects with improved (+1 or better) score on I-GAIS for either buttock or either thigh at Day 90 will be summarized by cohort using appropriate summary statistics and its 95% confidence interval will be provided.

All secondary and exploratory efficacy endpoints will be summarized using appropriate descriptive statistics by time point and cohort.

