1 PROTOCOL SUMMARY

1.1 Synopsis

Name of Sponsor/Company: DMR Research, PLLC Sponsor: Endo Pharmaceuticals Inc.

Name of Investigational Product: Qwo CCH

Name of Active Ingredient: Collagenase clostridium histolyticum

Title of Study: Treatment of 5 subjects to assess the effectiveness of multiple dose, multiple concentrations of clostridium histolyticum-aases, QWO, for the treatment of mild to moderate cellulite in adult females to the buttocks and thighs.

Phase of development: 4

Lead Principal Investigator: [name] [name]

Study period:

Estimated date first subject enrolled: 15Feb2021 Estimated date last subject completed: 15May2021

Objectives and Endpoints:

objectives and Endpoints.				
Objectives	Endpoints			
Primary				
To assess the effectiveness of multiple dose, multiple concentrations of clostridium histolyticum-aases for the treatment of mild to moderate cellulite in adult females to the buttocks and thighs	The proportion of subjects with improved (+1 or better) score on the Investigator Global Aesthetic Improvement Scale (I-GAIS) for buttock and thigh at Day 90.			
Secondary				
To evaluate effectiveness of CCH-aaes in individuals when concomitantly treating the buttock and the thigh in one treatment session	The proportion of subjects with improved (+1 or better) score on I-GAIS for either buttock or either thigh on Days 22, 43, and 90.			
To assess subject satisfaction with CCH treatment of buttock or thigh cellulite in adult females.	Mean change from baseline in Body-Q Appraisal of Cellulite ^d to Day 90.			
To generate calculations to determine a matrix of buttock and thigh injections possible from a single 1.84 mg vial	Dilution matrix used in clinical settings.			

Overall Design:

This is a single center, off-label, multiple dose, multiple injection areas, Phase 4 study to assess the safety and efficacy of multi-dilution CCH in adult women with mild or moderate edematous fibrosclerotic panniculopathy (EFP). 5 subjects will be screened and dosed in the buttock and thigh areas using a multi-dilution injection technique.

Qualified subjects (determined by investigator assessment) will receive a single vial of 0.84 mg of CCH to treatment areas (buttocks and thighs) for a total dose of 1.68 mg in both buttocks and both thighs per treatment session \times 3 treatment sessions (Day 1, Day 22, and Day 43). Subjects will have follow-up visits at approximately 90 after Day 1.

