9.2.7 Investigator Global Aesthetic Improvement Scale

Investigators who are physicians will use the I-GAIS to determine the degree of improvement of each buttock or thigh by comparing the cellulite from the Day 1 pretreatment (baseline) outcome image of each buttock or each thigh to the images taken at the subsequent visits specified in the Schedule of Activities. In visits where both I-GAIS and CR-PCSS are scheduled, I-GAIS assessment will occur after the CR-PCSS assessment to avoid introducing potential bias to the static CR-PCSS assessment by the investigator.

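### The primary endpoint requires buttock and thigh in the objectives, but Section 10.3.1 analyses an either/or version of it, by cohorts the study does not have

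*Protocol*

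**What the plan says.** - **Synopsis (1.1), primary endpoint:** the proportion of subjects with an improved (+1 or better) "score on the Investigator Global Aesthetic Improvement Scale (I-GAIS) for buttock and thigh at Day 90".
- **Section 3, primary endpoint:** the row is partly lost in the text at hand, but its legible part agrees: "score on the Investigator Global Aesthetic Improvement Scale. (I-GAIS) for buttock and thigh".
- **Synopsis and Section 3, first secondary endpoint:** an improved "score on I-GAIS for either buttock or either thigh on Days 22, 43, and 90".
- **Section 10.3.1:** the primary efficacy endpoint is the proportion with an improved "score on I-GAIS for either buttock or either thigh at Day 90 will be summarized by cohort using appropriate summary statistics", with a 95% confidence interval. Secondary and exploratory endpoints are also to be summarised by cohort.
- **Design (synopsis):** "5 subjects will be screened and dosed in the buttock and thigh areas". Section 7.5 describes an open-label, nonrandomized study, and Section 10.1 gives 5 as the sample size.
- **Section 10.4:** the only cohort named anywhere is a thigh cohort, called Cohort 1, of which about the first 40 subjects trigger an interim analysis. Its primary is an improved "score on I-GAIS for either thigh at Day 90".
- **Section 9.2.7:** the I-GAIS is used "to determine the degree of improvement of each buttock or thigh by comparing the cellulite", so a subject can have up to four ratings at a visit.

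**The concern.** The endpoint that 10.3.1 calls primary is, at Day 90, the same quantity as the first secondary endpoint. The primary endpoint in the objectives therefore has no analysis, and nothing in the protocol says which version prevails.

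The direction of the change matters. Section 2.1 states the purpose: to treat buttock and thigh in the same session without compromising effectiveness. Section 4.1 describes the buttock treatment as on label and given first; the thigh receives the further-diluted remainder. An either/or rule can be met by a buttock alone, so it can report success while the newer part of the procedure fails. The study plans no test, so this proportion and its interval are its main result. Ratings are open label and made by investigators, so an unsettled definition could be settled after the ratings are known.

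**Working it through.** **1. The texts side by side**

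| Place | Role | Rule across regions | Time | Grouping |
|---|---|---|---|---|
| 1.1 | Primary | buttock and thigh | Day 90 | none |
| 3 (legible part) | Primary | buttock and thigh | not legible | none |
| 1.1 and 3 | First secondary | either/or | Days 22, 43, 90 | none |
| 10.3.1 | Primary | either/or | Day 90 | by cohort |
| 10.4 | Interim primary | either thigh | Day 90 | Cohort 1 (thigh), about 40 subjects |

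The row for 10.3.1 matches the secondary endpoint, not the primary. The wording makes sense in a design with one region per cohort, where either thigh means left or right. Here every subject has both regions treated. Without cohorts, the literal rule is improvement in any one of four areas.

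**2. Gap between the rules, with no assumed rate**

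Take the objectives' version to mean at least one buttock and at least one thigh improved. Then

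P(either region) − P(both regions) = P(exactly one region improves).

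With n = 5, each subject who improves in exactly one region contributes 1/5 = 20 percentage points. Exact (Clopper-Pearson) 95% intervals for n = 5:

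| Discordant subjects | Either/or rule | Joint rule |
|---|---|---|
| 0 | same as joint | same as either/or |
| 1 (example) | 4/5: 28.4% to 99.5% | 3/5: 14.7% to 94.7% |
| 2 (example) | 4/5: 28.4% to 99.5% | 2/5: 5.3% to 85.3% |
| 5 (all improve in a buttock, none in a thigh) | 5/5: 47.8% to 100% | 0/5: 0% to 52.2% |

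**3. Illustration with assumed rates**

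Section 10.4 mentions a thigh responder rate t = 0.60, in text that does not fit this study. A buttock rate b = 0.70 is an assumption.

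- P(both) lies between b + t − 1 = 0.30 and min(b, t) = 0.60.
- The gap is b + t − 2·P(both), so it lies between 1.30 − 1.20 = 0.10 and 1.30 − 0.60 = 0.70.
- Under independence P(both) = 0.70 × 0.60 = 0.42 and P(either) = 1 − 0.30 × 0.40 = 0.88, a gap of 0.46.
- With b = 0.60 instead, the smallest possible gap is 0.

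**4. The objectives' wording is itself open**

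Assume 60% response in each of the four areas, independently (again an assumption):

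- any of four: 1 − 0.4⁴ = 97.4%
- at least one buttock and at least one thigh: (1 − 0.4²)² = 70.6%
- all four: 0.6⁴ = 13.0%

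In a simulated one-factor normal model, raising the between-area correlation from 0.3 to 0.8 moves these to 92% to 77%, 67% to 62%, and 23% to 41% respectively. Copying the objectives' phrase into 10.3.1 would therefore not be enough.

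**The case against.** The best defence is that by cohort can be read as by region, since 10.4 equates Cohort 1 with thigh. Section 10.3.1 would then give one proportion for the buttocks and one for the thighs. If the objectives' wording also means one proportion per region, the texts nearly agree and thigh failure is not hidden. But this needs a meaning of cohort that the protocol never gives, and a named cohort of about 40 subjects cannot exist in a study of 5. At most it shows that the sentence is ambiguous, and an ambiguous primary endpoint still has to be corrected.

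Second, how left and right combine, and how a subject rated in only one region is counted, can be left to an analysis plan. The evaluable population asks only that subjects "have at least 1 I-GAIS evaluation" besides one injection, which is an ordinary definition. That is fair: these are details to settle along the way, and the contradiction does not rest on them. Deferral does not resolve the contradiction itself. Section 10.3 promises the analysis plan before the interim analysis, and the trigger for that analysis cannot be reached with 5 subjects.

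Third, the study is exploratory, has no success threshold, and the intervals in the examples overlap heavily. The separate area ratings are collected, so information is masked in the headline result rather than lost. All of this stands and limits the harm. The assumed-rate figures are wide and only illustrative, and the identity in step 2 holds only for the at-least-one-of-each reading. The 20 points per discordant subject need no assumed rate.

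**Conclusion.** The primary endpoint is wrong as written. Sections 1.1 and 10.3.1 contradict each other, the legible part of Section 3 sides with 1.1, and the cohort reference has nothing to refer to in a single-group study of 5. Taken literally, 10.3.1 makes the primary a best-of-four-areas rule that a buttock alone can satisfy, against the stated purpose. On the at-least-one-of-each reading, the reported proportion is higher by 20 percentage points for every subject who improves in only one region: from no difference if there are none, to 5/5 against 0/5 in the extreme case. How many such subjects there will be cannot be predicted from the protocol. Because this proportion is the study's main result, the correction should be made before any Day 90 ratings.

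**What to change.** 1. Use one primary definition, word for word, in 1.1, 3 and 10.3.1, and make it fit the two-region objective. One option is a subject-level responder with at least one buttock and at least one thigh improved at Day 90. Another is two primary proportions, one per region. These are different quantities, so the protocol must name one.
2. State how left and right ratings combine, and how a subject without a Day 90 rating in one region is counted.
3. Delete the cohort references from both sentences of 10.3.1.
4. Keep the either/or version as the secondary endpoint only.
5. Whichever definition is chosen, report the Day 90 buttock and thigh proportions separately with exact 95% intervals.

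The cost is one or two sentences in the protocol and two table rows from ratings already planned, with no extra subjects or visits. The headline proportion will probably be less favourable: with complete ratings, neither the joint proportion nor either region's own proportion can exceed the either/or proportion.
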